5.4 Handling Missing Data

Missing data will be handled with two approaches: (1) minimizing the chance of missing data in the study design and conduct stages, and (2) handling missing data with statistical methods in the analysis phase.

The following measures will be taken to reduce missing data in the study design.

PrismRA arm: Missing data will be minimized through rigorous conduct of data collection as described in Section 8.9 of the Protocol. See below for the handling of missing follow-up data.

External control arm: At least one observed CDAI measurement in the 3-month period prior to the index date (b/tsDMARD initiation) and at least three observed CDAI measurements in the 12-month period prior to the index date (including the measurements in the aforementioned 3-month period) will be required to ensure patients are selected from practices where CDAI are recorded as a part of routine care.

The following statistical methods will be considered in handling missing data in the analyses.

The rigorous design of the study aims to reduce the amount of missing data in baseline variables. If needed, single imputation [8] of missing baseline characteristics will be used to ensure that all eligible patients are included in the PS model to estimate the probability of treatment [9] for confounding control. Further details of the treatment PS methods are described below in Section 6.3.

Longitudinal outcomes may be unobserved due to patients that are lost-to-follow up ("drop-out"), missed scheduled visits (PrismRA arm), encounters that fall outside of the specified follow up window (external control arm) or not measured during a completed visit. It is anticipated that at 24-weeks roughly 45% of the PrismRA arm and 50% of the external control arm will be missing outcome data. Within each study arm the number and proportion of missing outcomes at

12 and 24-week visits will be described and baseline characteristics of patients with complete versus incomplete outcome data will be compared.

For the primary efficacy analysis multiple imputation (MI) will be used with the assumption that patients with unreported outcome measures at 12 and 24 weeks have outcome events that are non-informative under the missing at random (MAR) assumption. This assumes that missingness occurs independent of the unobserved outcome: that is, the possibly unknown true outcome for a patient is the same regardless of whether it is actually observed. This assumption underlies the ITT principle, which analyses all eligible patients according to the treatment group to which they were assigned regardless of subsequent missingness.

For all approaches using MI, fully conditional specification (FCS) methods will be used, which assume the existence of a joint distribution for all variables. [10] All eligible patients meeting inclusion and exclusion criteria and initiating the study treatment will be used to impute missing observations. Imputation models will include all relevant available observations at baseline and 12 and 24 week follow up visits. Separate MI models will be used to create m imputed datasets for each study arm and combined into m analysis datasets with complete data. The choice of m will be determined by the fraction of missing information in the variables to be imputed. [11] MI performed separately within each study arm maintains the structure of the missing data patterns and the relationship between covariates specific to each database and ensures that no outcome information is used in PS matching. [12] Each imputation model will include all covariates listed in Table 4 of Section 6.2 along with the dependent variables and continuous scores for each study outcome as specified in Section 3.0. Dichotomous endpoints will be derived based on continuous scores within each imputed dataset. Analyses will proceed as described in Sections 6.3 and 6.4 using each of the imputed datasets. Finally, treatment effect estimates will be averaged using Rubin's rule [13] to obtain a pooled estimate with standard errors.

5.5 Statistical Bias Reduction

Studies using observational data are prone to multiple biases. These potential biases in this study are addressed as described below.

Selection Bias. To minimize selection bias for identifying an external control arm for a clinical trial, the study was designed using the target trial emulation framework. [14] The external control arm inclusion/exclusion criteria are carefully defined and matched to the PrismRA arm to reduce potential selection bias. All available patients in the external control arm meeting the criteria for selection will be used in the analyses.

The design of the study is aimed to emulate a randomized clinical trial as closely as possible. In a randomized clinical trial, on average, treated and control groups are balanced with respect to pre-treatment characteristics. The analysis of the entire randomized sample will give the unbiased estimate of the causal effect in the entire trial eligible population. Any "selection" of individuals after randomization could lead to covariate imbalance, change in the population for whom the result may apply, and biased treatment effect estimates. PS methods attempt to emulate the process of randomization by using only pre-treatment covariates (blinded to outcomes and other follow-up observations) to control for potential confounding. We propose a PS model building

process that will estimate a PS for each patient in the entire eligible cohort to be used in analyses of all study objectives.

Information bias. Observational studies relying on retrospective data collection are at risk of information bias, as the accurate assessment of exposures, outcomes and key covariates may be challenged by issues such as the timing of clinical assessments, criteria for treatment response, and documentation in the EMR that vary between and within sites. Objective measures of outcomes and other variables at predefined time points will be used where possible. All data for eligible patients will be extracted and data from multiple sources will be deterministically linked to create a more complete capture of the patient journey. For the external control arm, information on confounders will be limited to data as it is documented in the patient's record.

Confounding. Within randomized controlled trials, an appropriate control group for comparison to treated patients for causal inference is constructed through randomization. [15] On average, due to randomization, treated and control groups are balanced with respect to pre-treatment characteristics and confounding bias in estimated treatment effects is largely avoided.

Confounding bias in observational studies arises because risk factors that are associated with the outcome of interest may also influence treatment decisions. Thus, a major assumption for the estimation of unbiased treatment effects is that after adjusting for pre-treatment covariates, potential outcomes are independent of the actual treatment received. PS methods are a way to estimate causal treatment effects conditional on pre-treatment characteristics. [9 16] Using logistic regression we can estimate the individual probability of being treated. This approach allows analyses with observational data to emulate randomization such that conditioning on the PS provides unconfounded treatment effects.

5.6 Interim Analysis

A single interim analysis will be conducted at the time of 50% PrismRA arm completion (first 300 enrolled have reached treatment initiation visit or have dropped out of the PrismRA arm). All data available in the PrismRA arm at the time of the interim analysis will be included, but clinical utility of the PrismRA will not be evaluated to protect the integrity of the study. The interim analysis will be restricted to baseline characteristics, data completeness, treatment decision impact, and physician questionnaire survey analyses. All interim analyses will be conducted by the Scipher Medicine team.

5.7 Programming Environment

Data will be queried and prepared using SQL. Analytic procedures and generation of tables for the final analysis will be performed using SAS (version 9.4 or higher; Cary, NC). Interim analysis will be performed using R version 4.2.1.

6.0 STATISTICAL ANALYSES

6.1 Patient Cohort

A detailed description of study procedures can be found in Section 8 of the protocol.

6.1.1 Inclusion Criteria

Table 2 shows the inclusion criteria that will be used prospectively in the PrismRA arm and the best approximation for the selection of comparable patients in the observational external control arm.

Table 2. Inclusion criteria by study arm

	PrismRA arm	External control arm
1	Patient is eighteen years of age, or older (≥ 18) at time of consent.	All patients are ≥ 18 years at the initiation of b/tsDMARDs (which can be the first ever b/tsDMARDs or subsequent b/tsDMARDs).
2	Patient must meet the criteria for RA as defined by the 2010 ACR/EULAR classification at Visit 1.	Patients are in the OM1 PremiOM RA dataset (See Section 5.2 Study Population of the Protocol).
3	Patient has active, moderate to high RA with a CDAI of >10 at Visit 1.	CDAI of > 10 based on the most recent CDAI assessed during the 3-month period prior to the b/tsDMARDs initiation.
4	Patient has swollen and tender joint count of ≥ 2 each, as determined by CDAI assessment at Visit 1 using a 28-joint count.	Swollen and tender joint counts of ≥ 2 each based on the most recent joint counts assessed during the 3-month period prior to the b/tsDMARDs initiation.

5	
Patient is eligible for treatment with any b/tsDMARD therapy at Visit 1 based on all of the following:
 
 • Investigator determination that patient satisfies clinical criteria • Patient consents to the use of non-csDMARD therapy during shared investigator-patient decision making • Absence of any financial or logistical limitations to the initiation of a b/tsDMARD therapy 	
External control arm will enroll b/tsDMARD initiators to ensure the treating rheumatologist determination of indication, patient consent, and financial/logistical feasibility.
 
The list of b/tsDMARDs approved for RA includes the following:
 
TNFα (infliximab, etanercept, certolizumab pegol, golimumab, adalimumab)
 
Interleukin-6 inhibitor (IL-6i) (tocilizumab, sarilumab)
 
IL-1β (anakinra)
 
T-cell co-stimulation inhibitor (abatacept)
 
B-cell depletion agent (rituximab)
 
Janus Kinase inhibitor (JAKi) (tofacitinib, baricitinib, upadacitinib)
 
Biosimilars/generics of these b/tsDMARDs will also be included.

6	
Concomitant treatments including but not limited to the following are permitted per standard of care:
 
 • Conventional synthetic DMARD (csDMARDs) (e.g., methotrexate, sulfasalazine, leflunomide, or hydroxychloroquine) • Non-steroidal anti-inflammatory drugs (NSAIDs) • Corticosteroids • Prednisone (or equivalent) at a stable \leq 10 mg per day for at least 2 weeks prior to Visit 1 • Intra-articular or parenteral corticosteroids \leq 2 weeks prior to Visit 1 	
Concomitant treatments per standard of care will be allowed and recorded.

7	Patient is willing and able to complete the informed consent process and comply with study procedures and visit schedule.	This criterion is not replicable with real world dispensing data and will not be used.
8	This additional point does not apply to the PrismRA arm.	
It requires ≥ 1 CDAI in the 3-month period prior to the b/tsDMARD initiation to ensure patients from practices where CDAI is routinely used and baseline CDAI is well defined in this 3-month window. Furthermore, ≥ 3 CDAI measurements in the 12-month period prior to the b/tsDMARD initiation will also be required. If we can retain enough patients to fully match the PrismRA arm, then ≥ 4 CDAI measurements in the 12-month period prior to the b/tsDMARD initiation will be required.
 
To ensure sufficient medical history information and past b/tsDMARDs usage history, it requires at least 12 months of enrollment in the database prior to the study treatment initiation. All history information prior to 12 months will also be utilized.

6.1.2 Exclusion Criteria

Table 3. describes the exclusion criteria that will be used prospectively in the PrismRA arm and their best approximation for the selection of comparable patients in the observational external control arm.

In addition to the exclusion criteria outlined below, this study will exclude patients in the external control arm that are managed by physicians participating in the PrismRA arm to avoid potential for contamination bias (e.g., erroneous inclusion of patients who received PrismRA). Patients whose study treatment initiation is managed by PrismRA physicians identified by National Provider Identifier (NPI) will be excluded from eligibility.

Table 3. Exclusion criteria by study arm

PrismRA arm	External control arm

1	Patient has any non-study limitation precluding patient receipt of the PrismRA test (e.g., financial, or logistical limitations).	It assumes patients who used b/tsDMARDs did not have such limitations that would have prevented the potential receipt of the PrismRA test had it been offered.
2	Concurrent treatment with an investigational product or use of an investigational product less than 4 weeks prior to Visit 1.	This criterion is not replicable with real world dispensing data and will not be used.
3	Patient cannot have participated in an observational study at least 4 weeks prior to Visit 1.	This criterion is not replicable in real-world data and will not be used.
4	The use of RA therapies outside of FDA-approved indication.	This criterion is not replicable with real-world dispensing data and will not be used.
5	Patient has been previously exposed to any non-TNFi b/tsDMARDs (FDA approved or experimental).	
Patients who have been previously exposed to any non-TNFi b/tsDMARDs any time during their history prior to the study treatment initiation will be excluded.
 
The list of non-TNFi b/tsDMARDs approved for RA includes the following:
 
IL-6i (tocilizumab, sarilumab)
 
IL-1i (anakinra)
 
T-cell co-stimulation inhibitor (abatacept)
 
B-cell depletion agent (rituximab)
 
JAKi (tofacitinib, baricitinib, upadacitinib)
 
The list of non-TNFi b/tsDMARDs not currently approved for RA includes the following:

		IL-23i (guselkumab, risankizumab, tildrakizumab, ustekinumab [IL-12/IL-23i]) IL-17i (secukinumab, ixekizumab, brodalumab)
6	Women who are known to be pregnant or breast-feeding or plan to get pregnant during the study.	Patients who have relevant pregnancy-related codes in the past 12 months or during the 24-week follow-up will be excluded.
7	Patient is currently receiving systemic antimicrobial treatment for viral, bacterial, fungal, or parasitic infection at the time of Visit 1.	Patients who received antimicrobial medications in the 30-day period prior to the b/tsDMARD initiation will be excluded.
8	Patient has any active, chronic, or recurrent invasive infection (e.g., listeriosis and histoplasmosis) and/or a viral infection, that based on the Investigator's clinical assessment, makes the patient an unsuitable candidate for the study. This includes hepatitis B virus (HBV) or hepatitis C virus (HCV), recurrent or disseminated (even a single episode) herpes zoster, disseminated (even a single episode) herpes simplex, or human immunodeficiency virus (HIV).	Patients with the relevant diagnostic codes for chronic, or recurrent invasive infections any time prior to the study treatment initiation will be excluded. This includes listeriosis, histoplasmosis, coccidioidomycosis, tuberculosis, non-tuberculosis mycobacterial infections, cryptococcosis, pneumocystis pneumonia, toxoplasmosis, HBV, HCV, varicella zoster virus (VZV), herpes simplex virus (HSV), HIV.
9	Patients with malignancy except non-melanoma skin cancer, localized prostate cancer treated with curative intent with no evidence of progression, low risk or very low risk (per standard guidelines) localized prostate cancer under surveillance/watchful waiting (without intent to treat), or carcinoma in situ of any type (complete resected).	Patients with cancer diagnostic codes any time prior to the study treatment initiation will be excluded. This includes all malignancies except non-melanoma skin cancer. Allowing for localized and cured cancers is not replicable in real-world data and will not be attempted.

10	Patients who are unable to understand the protocol and unable to provide informed consent.	This criterion is not replicable in real-world data and will not be used.
11	Patients who are not indicated for PrismRA.	
This criterion is not replicable in real-world data and will not be used.
 
This study assumes that the careful replication of the above inclusion and exclusion criteria will ensure a comparable indication for PrismRA in the external control arm.

12	This point does not apply to the PrismRA arm.	Patients cared for by rheumatologists who have participated in the PrismRA arm any time in the past will be excluded to avoid including patients using PrismRA.

6.2 Demographics and Baseline Characteristics

The OM1 team will identify an eligible pool of patients for an external control arm in the OM1 PremiOM RA dataset.

The baseline study data from the PrismRA arm will be provided by the Scipher Medicine team in a format ready for analysis (fully quality controlled), with a corresponding dataset specification document to help the OM1 team understand the data.

From the pool of the study-eligible RA patients in the OM1 PremiOM RA dataset, the external control patients based on propensity score matching will be selected.

Baseline covariates including the following listed in **Table 4** will be considered (defined in a 6-month window prior to the index date unless otherwise specified elsewhere).

Table 4. Baseline covariates

Domain	Variables
Patient Characteristics	
 • Age (calculated from birth year) • Sex • Race/Ethnicity • Geography • Body mass index

Lifestyle	
 • Smoking (current, former, or never smoker)
Comorbidities (based on at least two diagnostic codes at least 30 days apart in the external control arm; based on an additional questionnaire in the PrismRA arm.)	
 • Lung disease • Myocardial infarction • Other cardiovascular • Stroke • Hypertension • Fractures spine, hip, or leg • Depression • Diabetes mellitus • Ulcer or stomach problem • Fibromyalgia 
The Rheumatic Disease Comorbidity Index (RDCI) will be derived.

RA Related	
 • Duration of RA (Defined as the number of days between the date of the first RA diagnosis code and the index date for the external control arm) • Seropositivity (rheumatoid factor or anti-citrullinated peptide antibody) • CDAI at baseline • Previous use of TNFi (yes, no)
Concurrent RA Medications	
 • Methotrexate • Folic acid • Non-methotrexate major csDMARDs (Sulfasalazine, Leflunomide, Hydroxychloroquine) • Glucocorticoids (with prednisone equivalent dose)

The choice of TNFi vs. non-TNFi b/tsDMARDs as the study treatment will be excluded from the list of potential propensity score variables, as this variable is temporally subsequent to the study's exposure variable (use or non-use of PrismRA in the PrismRA arm and external control arm, respectively) and is considered a mediator of the potential benefit of PrismRA.

In addition to the adjustment covariates, the following socioeconomic variables will be used for descriptive purposes among those who have non-missing values: household income, housing status, education, reduced employment status (e.g. employed, unemployed/disabled, student, retired, other/unknown), insurance, usual place of care (PrismRA arm).

The baseline characteristics of patients will be compared across the PrismRA arm and the external control arm both before and after the PS modelling procedure in a table. In general, each continuous variable will be reported as mean, standard deviation (SD) or median, interquartile range (IQR), and range where appropriate. Each categorical variable will be summarized as a number and proportion. The baseline characteristics after propensity score modeling will be examined for improved covariate balance via the absolute standardized mean metric for each covariate.

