4.0 DEFINITIONS

Terms	Definition of Terms
DRIVE Study	The comparative effectiveness study of the PrismRA test comparing the clinical outcomes of patients in the PrismRA arm (trial) and the external control arm (observational).
Baseline	Assessments of patients as they enter the PrismRA arm. For the external control arm, the corresponding baseline CDAI assessment window is the 3-month period before the index date (defined as the time of study treatment initiation). For medical history all available data before the index date will be used in the external control arm.
Enrollment	The point at which the patient signs the informed consent form for the PrismRA arm. Not applicable for the external control arm.
PrismRA arm	Trial participants in the trial conducted by Scipher Medicine for whom PrismRA test is performed and the Investigator will use the PrismRA test results to inform the treatment decision.
External control arm	OM1 real-world data patients who received standard of care treatment for RA with TNFi or non-TNFi b/tsDMARDs without guidance from PrismRA test results.

Terms	Definition of Terms
Study Treatment	The b/tsDMARDs (FDA approved for RA) that is initiated at Visit 2 (See Protocol Section 8.5) informed by the PrismRA test in the PrismRA arm and as a part of standard of care in the external control arm. This study treatment (b/tsDMARDs) can be the very first b/tsDMARD for the patient or a subsequent b/tsDMARD after having used one or more TNFi bDMARDs (but not non-TNF β b/tsDMARDs).
Study Treatment Initiation	The point at which a study treatment (See “Study Treatment” above) is initiated to treat RA. This time point constitutes the index date (beginning of the follow-up) and defined as Visit 2
RA Disease Activity	
Disease activity is based on the CDAI score as follows:
 
 • Remission: CDAI \leq 2.8 • Low: CDAI > 2.8 and \leq 10.0 • Moderate: CDAI > 10.0 and \leq 22.0 • High: CDAI > 22.0 
For the PrismRA arm, the CDAI scores will be assessed by the Investigator. The CDAI scores for the external control arm in OM1 PremiOM RA consist of CDAI scores in structured EMR data, and CDAI scores estimated by machine learning based on unstructured data.^[7] CDAI scores from all data sources will be used.

TNFi-naïve subgroup	Patients who have never taken a TNFi prior to visit 2.
TNFi-exposed subgroup	Patients who had received at least one TNFi prior to visit 2.

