The data source for the analysis is the OM1 PremiOM RA Dataset within the OM1 Real-World Data Cloud (RWDC [OM1, Inc, Boston, MA, US]). The OM1 RWDC is derived from deterministically linked, de-identified, individual-level health care claims, electronic medical record (EMR), and other data. EMR data are from sources geographically representative of the U.S. population and include medication history and prescription information, laboratory results, and diagnoses as documented by a physician. Additional medical and pharmacy claims data are linked to the clinical data to fill gaps in patients' clinical care. The medical and pharmacy claims contain billing and coding history on inpatient and outpatient encounters from acute care facilities, ambulatory surgery centers, and clinics. The OM1 RWDC includes data from January 2013 to present day.

To qualify for the OM1's PremiOM RA dataset, each patient must be at least 16 years old at the time of the qualifying diagnosis and meet at least one of the following conditions:

- At least two diagnosis codes for RA, at least 30 days apart, each coming from an encounter with a rheumatologist
- At least one inpatient RA diagnosis code
- At least two outpatient RA diagnosis codes, at least 30 days apart and within a year, regardless of physician specialty
- At least one outpatient RA diagnosis code and a prescription or fill for a DMARD and no diagnosis for any of the non-RA conditions for which those drugs may also be prescribed

Non-RA conditions are defined as juvenile idiopathic arthritis, psoriatic arthritis/psoriasis, ankylosing spondylitis, Crohn's disease, ulcerative colitis, hidradenitis suppurativa, cryopyrin-associated periodic syndromes, renal transplant, malaria, systemic lupus erythematosus, giant cell arteritis, cytokine release syndrome, all cancers, hydatidiform mole.

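### Control RA duration and prior TNFi status are cut off where the database record starts, and PrismRA duration is undefined, so matching can pair unlike patients without the balance checks showing it

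*SAP*

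**What the plan says.** SAP 6.2, Table 4 (and Protocol 10.3) lists RA duration as a matching covariate and defines it for one arm only: the "number of days between the date of the first RA diagnosis code and the index date for the external control arm". The PrismRA arm has an RA medical history entry at Visit 1 (Protocol 8.6), but neither document says how duration is derived from it.

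Prior TNFi use is a yes/no item in the same table, with no source given for either arm. The subgroup definition in SAP 4.0 is a lifetime one: "Patients who have never taken a TNFi prior to visit 2". SAP 6.3 uses this status to form the strata in which the propensity score is fitted and patients are matched, and SAP 7.0 uses it for the subgroups.

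For controls, SAP 6.1.1 requires "at least 12 months of enrollment in the database prior to the study treatment initiation" and adds that "All history information prior to 12 months will also be utilized". SAP 4.0 agrees: "For medical history all available data before the index date will be used in the external control arm". SAP 5.2 sets the outer limit: "The OM1 RWDC includes data from January 2013 to present day". Table 4 covariates are by default "defined in a 6-month window prior to the index date unless otherwise specified elsewhere".

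**The concern.** A first diagnosis code can be found only after the patient enters the data. A control with 12 years of RA and 18 months of record would enter the propensity model with 1.5 years. A control whose TNFi ended before the record began would be labelled naive. The lifetime definition in SAP 4.0 becomes, for controls, no TNFi seen in the record. The control exclusion for earlier non-TNFi b/tsDMARDs (SAP 6.1.2, row 5) has the same limit.

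The plan judges the propensity model by standardized differences on recorded values, with 0.1 as the threshold. If a variable measures different things in the two arms, a small difference shows only that the recorded numbers agree. At stake are the main odds ratio and, more directly, the TNFi-naive subgroup, because misclassified controls enter that stratum.

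No planned analysis addresses this. The committed sensitivity analysis restricts to complete CDAI scores (SAP 6.3.2, 6.4.2). The optional analyses in SAP 8.0 concern missing outcomes. Protocol 11 discusses data recency and RA identification, but not look-back.

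**Working it through.** The plan gives no figure for this error. Step 1 uses its dates; steps 2 to 4 are illustrations on stated assumptions.

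**1. Possible look-back.** The floor is 1.0 year (SAP 6.1.1). The ceiling is index date minus January 2013. The earliest historical index date allowed by SAP 5.2 is three years before March 2022, that is March 2019, which gives 6 years 2 months (6.2 years). An index date of March 2022 gives 9 years 2 months (9.2 years). Recorded control duration is therefore generally capped between 1 and about 9 years, depending on entry to the data.

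**2. Share of control durations truncated.** Assume true duration T is exponential with mean μ in both arms and look-back L is uniform on (a, b) years. Recorded control duration is min(T, L). Then P(T > L) = μ(e^(−a/μ) − e^(−b/μ))/(b − a). For μ = 7, a = 1, b = 9: 7 × (0.867 − 0.276)/8 = 52%.

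| Mean true duration | L 1–9 y | L 1–6 y | L 3–9 y |
|---|---|---|---|
| 2 y | 15% | 22% | 7% |
| 3 y | 25% | 35% | 16% |
| 5 y | 41% | 52% | 32% |
| 7 y | 52% | 62% | 44% |
| 10 y | 62% | 71% | 56% |

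With look-back starting at the guaranteed one year, the range is 15% to 71%.

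**3. Effect within recorded-duration bands** (simulation; PrismRA duration taken as exact, which is an assumption):

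| μ, L | Recorded band | True mean, PrismRA | True mean, control |
|---|---|---|---|
| 7, 1–9 y | 0–2 y | 0.95 | 3.2 |
| 7, 1–9 y | 2–5 y | 3.4 | 7.2 |
| 7, 3–9 y | 0–2 y | 0.95 | 0.95 |
| 7, 3–9 y | 2–5 y | 3.4 | 6.7 |
| 3, 1–9 y | 2–5 y | 3.3 | 4.2 |
| 2, 1–9 y | 2–5 y | 3.1 | 3.6 |

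In the second row, about 44% of the controls truly have 5 years or more. A longer look-back clears the short-duration band but barely changes the next one.

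**4. Effect of TNFi misclassification on the primary proportion.** Let m be the share of recorded-naive controls who are truly exposed, and g the response gap between naive and exposed patients. With no true effect, the spurious difference is b = m × g. The documents give neither input; I took m = 5% to 30% and g = 5 to 15 points. Then b runs from 0.05 × 5 = 0.25 points to 0.30 × 15 = 4.5 points, against the 10-point design difference.

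For the false-positive rate I used the plan's evaluable numbers: 600 × 0.55 = 330 and 1,500 × 0.50 = 750 (SAP 5.1). At these sizes Fisher's exact test has 88.4% power for 40% versus 30%, so the stated 88% reproduces. Now set the PrismRA rate at 30% and the control rate at 30% − b. For m = 20%, g = 10 points: b = 2.0 points, control rate 28%, pooled rate (99 + 210)/1,080 = 0.286, null SE 0.0299, alternative SE 0.0301. The upper-tail rejection probability is 1 − Φ((1.96 × 0.0299 − 0.02)/0.0301) = 10.0%. Adding 0.45% in the lower tail gives 10.5%. Across the grid the two-sided rate is 5.1% to 33.9%, against a nominal 5%. This treats the whole matched sample as recorded-naive; the bias shrinks in proportion to the naive stratum's real share.

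**The case against.** The strongest reply is that the plan already looks back as far as it can. Twelve months is a floor, and SAP 4.0, SAP 6.1.1 and Protocol 8.1 all call for the entire available history, including past medication. The source links EMR drug history, prescriptions and claims (SAP 5.2), so a TNFi stopped before enrollment may still be recorded. SAP 5.5 admits that control confounders are limited to what is documented. All of this stands, and it may recover much of the prior TNFi use. It does not repair duration, which the SAP ties to the first code whatever the chart says.

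Two further objections stand. First, a reader might infer that PrismRA patients supply a complete history. The documents show only a history item at Visit 1; the supportable statement is that duration in that arm is undefined. Second, the error need not run one way for duration. Protocol 11.2 cites a positive predictive value of 86.2% to 88.9% for code-plus-DMARD algorithms, so some first codes may be wrong and precede true RA. Record-start truncation itself can only shorten duration and hide exposure.

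Finally, the illustrations depend on their inputs. A mean true duration of 2 or 3 years gives much smaller contrasts than 7, and the documents supply no duration distribution.

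**Conclusion.** The concern holds as a defect of definition that can bias the comparison, not as a demonstrated bias. As written, control duration and TNFi-naive status are limited by where the record starts, PrismRA duration has no definition, and balance on recorded values cannot detect a mismatch. It is tempting to conclude that matching will pair early or truly naive PrismRA patients with long-standing or exposed controls. The documents do not support that certainty, because how often it happens depends on a look-back distribution they do not report.

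The direction favours PrismRA only if longer disease or prior TNFi use lowers response, which is assumed. On the assumed inputs, truncation affects 15% to 71% of controls with look-back from one year, and TNFi misclassification adds 0.25 to 4.5 points. Confidence is high for the definition gap and low for the size. The stated power is unaffected. The point should be fixed before matching.

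**What to change.** In SAP 6.2 and 6.3:

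1. Define RA duration and prior TNFi use, with the source, separately for each arm. For controls, take the diagnosis or onset date and earlier b/tsDMARD use charted in the EMR where recorded, and the first code date only otherwise. State that prior TNFi use draws on all available history, not the six-month default.
2. Flag code-based control durations that begin near record start as lower bounds. Enter duration in both arms in common categories with an open top category, or put the flag in the propensity model. The categories are safer: a flag that can occur only in controls predicts arm perfectly and would in effect drop those controls. Do not set flagged values to missing and singly impute them. With mean 7 and look-back 1–9 years, controls whose first code falls in their first 12 months of record have a true mean of 10.3 years and a recorded mean of 4.2, while unflagged controls average 2.2. Imputing from the latter moves values further from the truth.
3. Pre-specify one re-matched sensitivity analysis of the primary endpoint and the TNFi-naive subgroup in controls with longer look-back, for example 36 months or more. State that it reduces TNFi misclassification and short-duration error but leaves long durations truncated (44% still truncated at 3–9 years with mean 7).
4. Report control look-back by matched stratum.

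The cost is SAP wording, some chart-data extraction, and one extra matched analysis with fewer controls. No new patients are needed.
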